6.2 Prophylactic Drug Use

Prophylactic pretreatment with acetaminophen and diphenhydramine before ONO-4538 administration is recommended for subjects who develop an infusion related reaction to a previous dose of ONO-4538.

7. Investigational Product Discontinuation Criteria

Subjects satisfying any of the following criteria in the treatment phase will be discontinued the investigational product and proceed to the follow-up phase.

1. The development of PD is identified by the principal or sub investigator according to the RECIST guideline (version 1.1).
2. A worsening of clinical symptoms attributed to disease progression occurs.
3. The subject develops Grade 2 or higher interstitial lung disease, regardless of the causal relationship to the investigational product.
4. Grade 2 or greater eye pain, or visual acuity reduced occurs whose causal relationship with the investigational product cannot be ruled out and does not improve to Grade 1 severity with local treatment.
5. Grade 3 or greater bronchospasm, hypersensitivity reaction, infusion reaction (e.g., pyrexia, chills, nausea, pain, headache, cough, pruritus, rash) or uveitis occurs whose causal relationship with the investigational product cannot be ruled out.
6. An adverse event or other events delay the administration of the investigational product by more than 6 weeks.
7. The investigator or sub-investigator otherwise determines that continuing to administer the investigational product is inappropriate due to an efficacy- or safety-related reason.

Even when Criterion 1 is applicable, investigational product treatment may be continued if it is determined through consultation with the sponsor that no worsening of clinical symptoms attributable to disease progression occurs, continued treatment is expected to provide a clinical benefit, and the investigational product can continue to be safely administered. If the investigational product is to be continued, the subject should first be consulted about his or her willingness to continue receiving treatment, and this process should be documented in the medical records. Laboratory tests will be frequently repeated and other measures taken to adequately ensure subject safety. Any subject who is

found to have again developed PD according to the RECIST guideline (version 1.1)based on a point where a decision is made to continue investigational product treatment must cease using the investigational product regardless of whether clinical symptoms have worsened or not.

8. Endpoints

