6. Unless medically necessary, vital signs will be measured no sooner than 2 days, and other tests will be performed no sooner than 8 days after the previous measurement.
7. Perform before administering the investigational product.
8. Other than weight.
9. Perform only in Cycle 4.
10. Perform only in Cycles 2, 4, 5, 7, and 9.
11. Perform only in Cycle 3.
12. Collect sample immediately before the completion of investigational product administration.
13. Perform every cycle (every 6 weeks) between Cycle 2 and 29 and every 2 cycles (every 12 weeks) after Cycle 30.

Table 4-3 Study schedule (for subjects completing the treatment phase)

Category	Study day	At end of treatment phase ⁶	Follow-up phase	
			28 days after final dose or on discontinuation 28 or fewer days after final dose ⁶	Follow-up ⁷
Allowable range (days)		-3 to +3	-7 to +7	-
Visit		V f-0	V f-1	V f-n
Pregnancy test ¹		○ ⁸	○	
Performance Status		○	○	
Vital signs/weight/percutaneous oxygen saturation		○	○	
Chest X-ray		○	○	
12-lead ECG		○ ⁸	○	
Hematology tests, blood biochemistry tests, urinalysis		○	○	
Immunology/hormone tests		○	○	
Serum drug concentration ²		○ ⁸	○	
Anti-ONO-4538 antibody ²		○ ⁸	○	
Diagnostic imaging (e.g., CT, MRI)		○	○	○
[REDACTED]	[REDACTED]	[REDACTED]	[REDACTED]	
	[REDACTED]	[REDACTED]	[REDACTED]	
	[REDACTED]	[REDACTED]	[REDACTED]	
Concomitant drugs/adverse events ⁵		←	→	

1. Women of childbearing potential will undergo urine pregnancy testing.
2. Perform only if the subject proceeds to the follow-up phase within 1 year after the start of investigational product administration (by Cycle 9). Collect sample if possible 6 to 12 weeks after the final investigational product dose.
[REDACTED]
[REDACTED]
5. Investigate all adverse events and concomitant treatments to the completion of the final tests (other than the survey for 'determination of outcome') specified in the protocol. Beyond the completion of the final tests (other than the survey for 'determination of outcome') specified in the protocol, follow any persisting adverse event for which a causal relationship with the investigational product cannot be ruled out, adverse events that resulted in discontinuation, and the concomitant treatments associated with those events until the events resolve, improve, or are determined to be permanent or no further follow-up is necessary. And all treatment-related adverse events will be followed every 2 weeks if possible.

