ONO-4538 is administered at a 3 mg/kg dose with a 2-week dosing interval. One cycle consists of 6 weeks. ONO-4538 administration will continue until the development of PD as identified by the investigator or sub investigator according to the RECIST guideline (version 1.1). The appropriate dose of ONO-4538 will be diluted with physiological saline or dextrose 5% in water to a total amount of approximately not less than 60 mL before use (so that the solution drug concentration is no less than 0.35 mg/mL). The entire dose of ONO-4538 will be administered as an intravenous infusion over approximately 60 minutes through a 0.20 ~ 1.20 μ m in-line filter. The lower limit of the infusion time is 54 minutes. The target upper limit is 90 minutes. At the end of the infusion, the line will be flushed with a sufficient quantity of physiological saline or dextrose 5% in water. The ONO-4538 dose will not be reduced. The administration of ONO-4538 infusion must be completed within 24 hours of preparation. If not used immediately, the infusion solution may be stored under refrigeration condition (2°-8°C, 36°-46°F) for up to 24 hours, and a maximum of 8 hours of the total 24 hours can be at room temperature (20°-25°C, 68°-77°F) and room light. The maximum 8-hour period under room temperature and room light conditions includes the product administration period.

The dose will be changed if the body weight of the subject changes by at least 10% relative to the weight at enrollment. Each subsequent 10% or greater change in body weight is to be handled in a similar manner.

6. Prior and Concomitant Therapies

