## **10 SAFETY EVALUATION**

Unless otherwise noted, safety data to be tabulated will be those observed during the period for 28 days after the final dose (or until the start of subsequent anti-cancer therapy for non-small-cell lung cancer after the final dose, whichever comes first).

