##### **2) Data Handling**

An adverse event is any unfavorable or unintended sign (including an abnormal laboratory finding), symptom or disease during a clinical trial, whether or not related to the investigational product. Of note, tabulation will include adverse events whose symptoms have occurred/worsened during the period from the first dose of the study drug until 28 days after the final dose (or until the start of subsequent anti-cancer therapy for non-small-cell lung cancer after the final dose, whichever comes first after the final dose). In addition, all adverse events that occur during the treatment period or the subsequent anti-cancer therapy follow-up period will be listed and reported.

All adverse events reported in this clinical study will be coded by SOC (System Organ Class) and PT (Preferred Term) using MedDRA (Current version). Treatment-emergent adverse events are those events that occur or worsen on or after the first dose of study treatment up until end of study treatment.

For the analysis of adverse events, only treatment-emergent adverse events (TEAEs) will be included in the summary tables.

In case the same adverse events in terms of SOC and PT occurs to one subject more than once, it will be considered as a single event, and the highest severity and relationship status among all events will be taken into account.

Severity of adverse events will be classified using NCI-CTCAE, and where NCI-CTCAE is inapplicable, it will be classified as grade 1 ('Mild'), grade 2 ('Moderate'), grade 3 ('Severe'), grade 4 ('Life threatening or disabling/incapacitating') or grade 5 ('Death related to adverse event') based on the maximum intensity. With respect to the relationship to study drug, 'Related' will be regarded as

related, and ‘Not related’ will be regarded as unrelated. If the relationship is unclear due to a missing, the relationship to study drug is considered as ‘Related’.

(1) Time to a Grade 3 or higher adverse event will be calculated using the following formula.

- Time to a Grade 3 or higher adverse event (days) = (date of the onset of the Grade 3 or higher adverse event, or the date of worsening to Grade 3 or higher, whichever comes first) - (the first dose date of investigational product) + 1

Data will be censored if the subject has no Grade 3 or higher adverse event at 28 days after the final dose (or at the start of subsequent anti-cancer therapy for non-small-cell lung cancer after the final dose, whichever comes first).

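### Safety tables close 28 days after the final dose, but a subject stopped for a dosing delay stays in the treatment phase at least 14 to 28 days longer, and events in that time count only if dosing resumes

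*Protocol*

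**What the plan says.** **Dosing and stopping.** Protocol section 5: "ONO-4538 is administered at a 3 mg/kg dose with a 2-week dosing interval". Under section 7, subjects who meet a criterion "will be discontinued the investigational product and proceed to the follow-up phase". Criterion 6 reads: "An adverse event or other events delay the administration of the investigational product by more than 6 weeks". The text does not say from which date the six weeks are counted.

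**Visits and collection.** Protocol Table 4-3 has an end-of-treatment visit, V f-0 (-3 to +3 days), and a post-treatment visit, V f-1 (-7 to +7 days), set at "28 days after final dose or on discontinuation 28 or fewer days after final dose". Footnote 5 says: "Investigate all adverse events and concomitant treatments to the completion of the final tests".

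**Safety window.** SAP section 10: "safety data to be tabulated will be those observed during the period for 28 days after the final dose", or until subsequent NSCLC therapy if that starts sooner. SAP 10.1.2 2) tabulates "adverse events whose symptoms have occurred/worsened during the period from the first dose of the study drug until 28 days after the final dose", with the same cut. Items (1) to (5) of that section carry the 28-day limit into the censoring of time to Grade 3 or higher and select events and into the death count. Section 10.2.3 4) carries it into the Grade shift table. The laboratory, immunologic and hormonal sections adopt the adverse event period.

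**A second end point.** SAP 10.1.2 2) also defines treatment-emergent adverse events (TEAEs) as ending with study treatment, does not say when that is, and admits only TEAEs to the summary tables. All events in the treatment or follow-up period go to a listing.

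**The concern.** The window is tied to the final dose, and during a hold nobody knows whether the last dose given was the final one. Suppose a new Grade 3 event begins on day 40 of a hold. If dosing resumes, a later dose becomes the final dose and the event is tabulated. If dosing never resumes, the window closed on day 28 and the same event is left to the listing. In the time-to-event analyses the first subject has an event and the second is censored event-free at day 28, although both were in the treatment phase on day 40.

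Whether treatment-phase time counts thus depends on a later outcome, which the event itself may influence. Compared with a window that runs to the end of the treatment phase, this can only lower the counts. Separately, the two end points in SAP 10.1.2 2) would let two programmers produce different adverse event tables from the same data.

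**Working it through.** The plan gives no figure of its own on this point, so there is none to reproduce. Take the last dose as day 0.

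**1. Inputs.** Dosing interval 14 days (Protocol section 5). Delay limit 6 weeks = 42 days (section 7). Table close at day 28 (SAP 10, 10.1.2 2), 10.2.3 4)). V f-1 range 28 - 7 = day 21 to 28 + 7 = day 35 (Table 4-3).

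**2. Earliest stop, and treatment-phase time outside the tables.** Stop = start of the delay count + 42. Untabulated time = stop - 28. Share = untabulated time / stop.

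| Delay counted from | Stop later than day | Untabulated, at least | Share | V f-1 range ended before stop by at least |
|---|---|---|---|---|
| Last dose (day 0) | 0 + 42 = 42 | 42 - 28 = 14 days | 14/42 = 33% | 42 - 35 = 7 days |
| Missed due date (day 14) | 14 + 42 = 56 | 56 - 28 = 28 days | 28/56 = 50% | 56 - 35 = 21 days |

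Two other starting points were tried. The 10-day minimum gap gives a stop after day 52, with 24 days (46%) untabulated. A due day at the end of the +7-day visit allowance (day 21) gives a stop after day 63, with 35 days (56%) untabulated. On every reading the stop comes after both the table close and the V f-1 range.

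**3. Is the event that started the hold lost?** It must begin by the time the next dose is missed, nominally day 14. At the widest visit windows the last dose is on Day 23 (29 - 6) and the next is due by Day 50 (43 + 7): 50 - 23 = 27. Onset is therefore by day 27, inside the 28-day limit. What falls outside is a new event, or a worsening to a higher grade, from day 29 on.

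**4. Is the 28-day assessment lost?** Not always. Footnote 6 of Table 4-3 accepts an earlier measurement made within the range. The Day 43 visit (Days 37 to 50) lies:
- 43 - 15 = 28 days after a last dose on Day 15 (22 to 35): inside the V f-1 range;
- 43 - 29 = 14 days after a last dose on Day 29 (8 to 21): touches the range only at day 21;
- 43 - 1 = 42 days after a last dose on Day 1 (36 to 49): outside.

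**5. The TEAE sentence.**
- If study treatment ends at the last dose, the summary tables close at day 0, against the 28-day text.
- If it ends on leaving the treatment phase and that sentence governs, events late in a hold are tabulated, again against the 28-day text.
- If it ends on leaving the treatment phase and both conditions apply, day 28 still limits.

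**6. Weight of one subject.** With the planned numbers, one subject is 1/41 = 2.4 points in the squamous cohort, 1/52 = 1.9 in the non-squamous cohort and 1/93 = 1.1 overall.

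**The case against.** A reader might infer that the toxicity that prevents re-dosing is the toxicity lost. The documents do not support that: by step 3 the event that starts the hold is within the 28-day limit, and SAP 10.1.3 2) (5) and (6) also provide tables of events leading to discontinuation and interruption.

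Three further inferences fail:
- **Deaths disappear.** Overall survival counts death from any cause with no 28-day cut (SAP 9.2.3 2)). Only the safety death count is windowed. A death during a hold after day 28 does miss that count.
- **Nothing from V f-0 is used.** Its imaging feeds response and progression-free survival, which have no 28-day limit, and SAP 4.3 lists the end of the treatment period as an accepted time point.
- **The lapsed V f-1 is uncovered.** Earlier in-range measurements may stand. Laboratory tests, vital signs, chest X-ray and Performance Status are done at V f-0, and footnote 8 moves the pregnancy test, ECG, drug concentration and antibody samples there when the 28-day tests were not done.

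Nor can these subjects be called those with the worst tolerability. Criterion 6 also covers delays for reasons other than adverse events, and other criteria can end treatment sooner.

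Two objections stand as limits. Each subject counts once per event term at the highest severity, so a subject already at Grade 3 or higher may add nothing to the overall Grade 3 count. A longer window for held subjects also makes observation time less equal across subjects. Neither removes the dependence on later re-dosing.

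**Conclusion.** The concern holds in a limited form. For a subject stopped under criterion 6, at least 14 of 42 days (33%) or 28 of 56 days (50%) between last dose and stop is treatment-phase time outside the safety tables. Which figure applies depends on where the delay is counted from. New or worsened events in that time are collected and listed. They are absent from the incidence tables, the worst-grade shift table and the time-to-event curves unless dosing resumes; the windowed death count has the same gap.

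This rests on the 28-day limit governing the tables, which the conflicting TEAE sentence leaves unsettled. The documents do not show how many subjects stop this way or how many have such an event, so the total effect is unknown and may be small. The change is worth making because the rule lets a later outcome decide what counts, and the data to correct it are already collected.

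**What to change.** **SAP.** In section 10, in 10.1.2 2) (including the TEAE sentence and items (1) to (5)) and in 10.2.3 4), use one end date for tabulation and censoring: the later of 28 days after the final dose and the date the subject leaves the treatment phase (V f-0), still cut at the start of subsequent NSCLC therapy. The TEAE sentence must change with the rest; otherwise the adverse event summary tables might not change. The laboratory, immunologic and hormonal analyses follow through their existing link to the adverse event period.

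**Protocol.** Reconcile the V f-1 timing in Table 4-3 with criterion 6 for subjects whose 28-day date has already passed, and state from which date the delay is counted. No clinical rule is proposed here.

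**Cost.** Revised SAP wording, one derived date and no new data. Subjects stopped after a hold get a longer window and slightly higher counts. Keeping the 28-day tables as a sensitivity version preserves comparability.

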8.1 Efficacy

1. Primary endpoint: Response rate (centrally assessed)
2. Secondary endpoints: Response rate (study site assessment by investigator), overall survival, progression free survival, time to progression, duration of response, time to response, best overall response, and percent change in tumor diameter

8.2 Safety

1. Adverse events
2. Laboratory tests (hematology, blood biochemistry, qualitative urinalysis, immunology tests, hormone tests)
3. Vital signs (systolic blood pressure/diastolic blood pressure, pulse, body temperature), body weight, percutaneous oxygen saturation (SpO₂)
4. 12-lead ECG
5. Chest X-ray
6. Performance Status (ECOG)

8.3 Pharmacokinetics

1. Serum ONO-4538 concentrations

8.4 Anti-drug Antibodies

1. Anti-ONO-4538 antibody

9. Planned Number of Subjects

Total of 93 subjects (41 subjects with squamous NSCLC and 52 subjects with non-squamous NSCLC)

10 Investigational Product Supply Restrictions

Each subject to whom the investigational product discontinuation criteria and individual subject discontinuation criteria are not applicable is eligible to receive the investigational product from the sponsor. The sponsor will stop supplying the investigational product if:

1. Ministry of Food and Drug Safety rejects the application for approval for the present indication.
2. The study is cancelled due to safety concerns.
3. The subject is able to receive the drugs through public or private health insurance.
4. An alternative therapy becomes available.

11. Planned Study Period

January 2014 to December 2021

The data cut-off may be performed based on progress of the clinical studies.

## History of Revision

Study No	ONO-4538-09	Sponsor	Ono Pharmaceutical Co., Ltd.	
Approval Date	Amended Version	Original	Amendment	Reason
09 Apr 2015	SAP_ONO-4538-09_version 2.0, 08 Apr 2015	
Section 1
 
ONO-4538 (Bristol-Myers Squibb [BMS] developmental code: BMS-936558, ex-Medarex developmental code: MDX-1106) is a fully human monoclonal antibody to human programmed cell death-1 (PD-1 [also known as CD279]), made by Ono Pharmaceutical Co., Ltd. and Medarex Inc. The product is made with recombinant technology using CHO cells. PD-1 is a receptor of the CD28 family (a molecular group that positively and negatively regulates the activation of T cells in supplementary fashion), which is expressed on activated lymphocytes (T cells, B cells and NKT cells) and myeloid cells. PD-1 binds to PD-1 ligands (PD-L1 [also known as B7-H1 and CD274] and PD-L2 [also known as B7-DC and CD273]), which are expressed on antigen-presenting cells, and transmits regulatory stimuli to lymphocytes to down-modulate the activation of lymphocytes. PD-1 ligand is also expressed in various human cancer tissues other than antigen presentation cells.
	
Changed to:
 
ONO-4538 (Bristol-Myers Squibb [BMS] developmental code: BMS-936558, ex-Medarex developmental code: MDX-1106) is a fully human monoclonal antibody to human programmed cell death-1 (PD-1 [also known as CD279]), made by Ono Pharmaceutical Co., Ltd. and Medarex Inc. In Japan, it obtained manufacturing and marketing approval for indications of unresectable malignant melanoma. PD-1 (or CD279), a 55-kilodalton Type 1 transmembrane protein, is a member of the CD28 family of T-cell co-stimulatory receptors that include immunoglobulin super family members CD28, CTLA-4, ICOS, and BTLA. PD-1 is highly expressed on activated T-cells and B-cells. PD-1 expression can also be detected on memory T-cell subsets with variable levels of expression. Two ligands specific for PD-1 have been identified: PD-L1 (also known as B7-H1 or CD274) and PD-L2 (also known as B7-DC or CD273). PD-L1 and PD-L2 have been shown to down-regulate T-cell activation upon binding to PD-1 in both murine and human systems. The product is made with recombinant technology using CHO cells.
	Protocol update
		
Section 3.2.2
 
6. Has a history of prior treatment with any of the following systemic anti-cancer products
	
Changed to:
 
6. Has a history of prior treatment with any of the following systemic anti-cancer agents
	Typo
		
Section 3.2.2 12
 
- AST (GOT) and ALT (GPT) ≤ 3.0 times the upper limit of normal range of each institute
 
- Total bilirubin ≤ 2.0 times the upper limit of normal range of
	
Changed to:
 
- AST (GOT) and ALT (GPT) ≤ 3.0 times the upper limit of normal range of each institute
 
- Total bilirubin ≤ 2.0 times the upper limit of normal range of
	Typo

		each institute	each institute	
		Section 3.2.3 Patients who meet any of the following criteria will be excluded	Changed to: Patients satisfying any of the following criteria will be excluded	Typo
		Section 3.3 Clinical Trial Schedule and Observations This clinical trial consists of the screening period, treatment period, and follow-up period, as is outlined in Figure 3.1.  Screening period Treatment period Post-treatment follow-up period  Figure 3.1 Schematic of the clinical trial design	Changed to: Study Schedule and Observations The study consists of the screening phase, treatment phase, and follow-up phase, as is outlined in Figure 3.1.  Screening phase Treatment phase Follow-up phase  Figure 3.1 Summary of study design	Typo
		Section 3.4 ONO-4538 is administered at a 3 mg/kg dose with a 2-week dosing interval. One cycle consists of 6 weeks. ONO-4538 administration will continue until the development of PD as identified by the investigator or sub investigator according to the RECIST guideline (version 1.1). The appropriate dose of ONO-4538 will be diluted with physiological saline to a total amount of approximately not less than 60 mL before use (so that the solution drug concentration is no less than 0.35 mg/mL). The entire dose of ONO-4538 will be administered as an intravenous infusion over approximately 60 minutes through a 0.20 µm in-line filter. The lower limit of the infusion time is 54 minutes. The target upper limit is 90 minutes. At the end of the infusion, the line will be flushed with a sufficient quantity of physiological saline. The ONO-4538 dose will not be reduced.	Changed to: ONO-4538 is administered at a 3 mg/kg dose with a 2-week dosing interval. One cycle consists of 6 weeks. ONO-4538 administration will continue until the development of PD as identified by the investigator or sub investigator according to the RECIST guideline (version 1.1). The appropriate dose of ONO-4538 will be diluted with physiological saline or dextrose 5% in water to a total amount of approximately not less than 60 mL before use (so that the solution drug concentration is no less than 0.35 mg/mL). The entire dose of ONO-4538 will be administered as an intravenous infusion over approximately 60 minutes through a 0.20 ~ 1.20 µm in-line filter. The lower limit of the infusion time is 54 minutes. The target upper limit is 90 minutes. At the end of the infusion, the line will be flushed with a sufficient quantity of physiological saline or dextrose 5% in water. The ONO-4538 dose will not be reduced. The administration of ONO-4538 infusion must be completed within 24 hours of preparation. If not used immediately, the	Protocol update

		infusion solution may be stored under refrigeration condition (2°-8°C, 36°-46°F) for up to 24 hours , and a maximum of 4 hours of the total 24 hours can be at room temperature (20°-25°C, 68°-77°F) and room light. The maximum 4-hour period under room temperature and room light conditions includes the product administration period.	
	Section 3.7.2  The threshold response rate (the null hypothesis) was set at 8.8% because the response rate of docetaxel, which was selected as a comparator in non-Korean Phase III studies (CA209017, CA209057), was 8.8% in the phase III trial in patients with NSCLC 7). Under the assumption of the threshold response rate of 8.8% and the expected response rate of 23.1% and 21.4% for patients with squamous and non-squamous NSCLC respectively,	Changed to:  The threshold response rate (the null hypothesis) was set at 8.8% because the response rate of docetaxel, which was selected as a comparator in non-Korean Phase III studies (CA209017, CA209057), was 8.8% in the phase III trial in patients with NSCLC. Under the assumption of the threshold response rate of 8.8% and the expected response rate of 23.1% and 21.4% for patients with squamous and non-squamous NSCLC respectively,	Typo
	Section 4.1 2) SAF  This set will be defined as group of subjects who included in ENR and have received at least one dose of the study drug.	Changed to:  This set will be defined as group of subjects who are included in ENR and have received at least one dose of the study drug.	Typo
	Section 4.3 1. Treatment Period Cycle 1  29	Changed to:  1. Treatment Period Cycle 1, Cycles 2 and beyond  29 c)	Typo
	Section 6.1	Added:  With regard to the analysis item (1) in 6.2 Analysis Items and Data Handling, the ENR will be the analysis set.	Add for clarifying the analysis set.
	Section 8.2  “TNM classification (screening), metastasis lesions and stage (screening)”  “NSCLC treatment history (surgical history, radiotherapy history, medication history, others)”	Changed to:  “TNM classification (baseline), metastasis lesions and stage (baseline)”  “NSCLC treatment history (surgical history, radiotherapy history, medication history, others, number of treatment regimens )”	Correct for ensuring consistency with protocol.

		
Section 8.3 1)
 
Change of classification :
 
“To be decided by data review”
 
“IIIB, IV, Recurrent, Unknown, Other”
 
“1, 2”
	
Changed to:
 
“Height : <160.0, 160.0-<170.0, ≥170.0”
 
“Weight: <55.0, 55.0-<65.0, ≥65.0”
 
“BMI: <18.5 ,18.5-<25.0 ,≥25.0”
 
“Time from diagnosis date of primary disease to first dose date of the investigational product: <180, 181-<360, ≥361”
 
“IIIB, IV, Recurrence, Unknown, Other”
 
“Yes, No”
 
Added:
 
“Item : NSCLC treatment History (Number of treatment regimens), Classification: 1, 2, Analysis method: Proportion by category”
	
Define classifications.

		
Section 8.3 2)
	
Added:
 
“NSCLC treatment history (medication) will be summarized. Agents and medication will be reported using the generic name.”
	
Add for evaluating the demographic in more detail.

		
Section 9.2.4 2)
 
“A Kaplan-Meier curve will be plotted for each analysis variable. The median and its 95% confidence interval will be estimated by Kaplan-Meier method.”
	
Changed to:
 
“A Kaplan-Meier curve will be plotted for each analysis variable. The median and its 95% confidence interval and overall survival rates at 6 months and its 95% confidence interval will be estimated by Kaplan-Meier method.”
 
Added:
 
“6 months will be calculated assuming 30.4375 days for one month.”
	
Add for evaluating the efficacy in more detail.

		
Section 9.2.4 3)
 
“Two Kaplan-Meier curve will be plotted based on the interpretation by the image central analysis laboratory and that by a investigator at the trial site. The median progression free survival, its 95% confidence interval and progression free survival rates at 3 and 6 months will be estimated by Kaplan-Meier method.”
	
Changed to:
 
“Two Kaplan-Meier curves will be plotted based on the interpretation by the image central analysis laboratory and that by an investigator at the trial site. The median progression free survival, its 95% confidence interval and progression free survival rates at 3 and 6 months and its 95% confidence interval will be estimated by Kaplan-Meier method. “
	
Add for evaluating the efficacy in more detail.

		
Added: "6 months will be calculated assuming 30.4375 days for one month."
	
	
Section 9.2.4 4) "The median and its 95% confidence interval will be estimated by Kaplan-Meier method."
	
Changed to: "The median and its 95% confidence interval and duration of response rates at 6 months and its 95% confidence interval will be estimated by Kaplan-Meier method."
 
Added: "6 months will be calculated assuming 30.4375 days for one month."
	Add for evaluating the efficacy in more detail.
	
Section 9.2.4 7)
	
Added: "In addition, a plot of individual subjects' percent change in tumor diameter of target lesion will be displayed at individual time point."
	Add for evaluating the efficacy in more detail.
	
Section 9.2.5 3)
	
Added: "and totality"
	Add for clarification.
	
Section 10
	
Added: "Unless otherwise noted, safety data to be tabulated will be those observed during the period for 28 days after the final dose (or until the start of subsequent anti-cancer therapy for non-small-cell lung cancer after the final dose, whichever comes first)."
	Add for evaluating the safety properly.
	
Section 10.1.2 2) An adverse event is any unfavorable or unintended sign (including an abnormal laboratory finding), symptom or disease during a clinical trial, whether or not related to the investigational product. Of note, tabulation will include adverse events whose symptoms have occurred/worsened during the period from the first dose of the study drug until 28 days after the final dose (or until the start of subsequent anti-cancer therapy for non-small-cell lung cancer, whichever comes first after the final dose).
	
Added: An adverse event is any unfavorable or unintended sign (including an abnormal laboratory finding), symptom or disease during a clinical trial, whether or not related to the investigational product. Of note, tabulation will include adverse events whose symptoms have occurred/worsened during the period from the first dose of the study drug until 28 days after the final dose (or until the start of subsequent anti-cancer therapy for non-small-cell lung cancer after the final dose, whichever comes first after the final dose).
	Add for evaluating the safety properly.
	
Section 10.1.2 2)
	
Deleted: "For event counting in such cases, the same adverse events
	Typo

		will be considered as different events."	
	Section 10.1.2 2) Severity of adverse events will be classified using NCI-CTCAE, and where NCI-CTCAE is inapplicable, it will be classified as grade 1 ('Mild'), grade 2 ('Moderate'), grade 3 ('Severe'), grade 4 ('Life-threatening or disabling') or grade 5 ('Death') based on the maximum intensity.	Changed to: Severity of adverse events will be classified using NCI-CTCAE, and where NCI-CTCAE is inapplicable, it will be classified as grade 1 ('Mild'), grade 2 ('Moderate'), grade 3 ('Severe'), grade 4 ('Life threatening or disabling/incapacitating') or grade 5 ('Death related to adverse event') based on the maximum intensity.	Correct for ensuring consistency with protocol.
	Section 10.1.3 1) (1)	Added: "and totality"	Add for clarification.
	Section 10.1.3 2) (2) "Adverse events will be summarized by SOC, PT and CTCAE grade. The data will be displayed as "subject number (incidence of subjects (%))"."	Changed to: "Adverse events and adverse drug reactions will be summarized by SOC, PT and CTCAE grade (grade 1, 2, 3, 4, and 5). The data will be displayed as "subject number (incidence of subjects (%))"."	Add for evaluating the safety in more detail.
	Section 10.1.3 2) (3) "Incidences of adverse events and adverse drug reactions by SOC and PT will be summarized according to Grade. In addition, incidences of Grade 3 or higher adverse events and adverse drug reactions will be summarized by SOC and PT."	Changed to: "Incidences of adverse events and adverse drug reactions by SOC and PT will be summarized. In addition, incidences of adverse events and adverse drug reactions will be summarized by SOC, PT and CTCAE grade (any grade, grade 3 or 4, grade 5). And adverse events and adverse drug reactions with an incidence at or above a certain level will be summarized by SOC, PT and CTCAE grade (any grade, grade 3 or 4, grade 5)."	Add for evaluating the safety in more detail.
	Section 10.1.3 2) (5) "Incidences of adverse events and adverse drug reactions leading to discontinuation of the study treatment will be summarized by SOC and PT."	Changed to: "Incidences of adverse events and adverse drug reactions leading to discontinuation of the study treatment will be summarized by SOC, PT and CTCAE grade (any grade, grade 3 or 4, grade 5)."	Add for evaluating the safety in more detail.
	Section 10.1.3 2) (6) "Incidences of adverse events and adverse drug reactions leading to interruption of the investigational product will be summarized by SOC and PT."	Changed to: "Incidences of adverse events and adverse drug reactions leading to interruption of the investigational product will be summarized by SOC, PT and CTCAE grade (any grade, grade 3 or 4, grade 5)."	Add for evaluating the safety in more detail.

	Section 10.1.3 2) (7) “Incidences of serious adverse events and adverse drug reactions will be summarized by SOC and PT.”	Changed to: “Incidences of serious adverse events and adverse drug reactions will be summarized by SOC, PT and CTCAE grade (any grade, grade 3 or 4, grade 5).”	Add for evaluating the safety in more detail.
	Section 10.1.3 2) (8) “Incidences of select, Grade 3 or higher, adverse events and adverse drug reactions will be summarized by categories and PT.”	Changed to: “Incidences of select adverse events and adverse drug reactions will be summarized by categories, PT and CTCAE grade (any grade, grade 3 or 4, grade 5).”	Add for evaluating the safety in more detail.
	Section 10.1.3 2)	Added: “(9) Incidences of select adverse events and adverse drug reactions leading to discontinuation will be summarized by categories, PT and CTCAE grade (any grade, grade 3 or 4, grade 5). (10) Incidences of serious select adverse events will be summarized by categories, PT and CTCAE grade (any grade, grade 3 or 4, grade 5).”	Add for evaluating the safety in more detail.
	Section 10.1.4	Added: “and totality”	Add for clarification.
	Section 10.2.3	Added: “and the change from baseline”	Add for evaluating the safety in more detail.
	Section 10.3.3 1)	Added: “and the change from baseline”	Add for evaluating the safety in more detail.
	Section 10.3.3 3)	Added: “and totality”	Add for clarification.
	Section 10.4.3 2) “Summary statistics (no. of subjects, mean, standard deviation, median, minimum, and maximum) will be provided for each Hormonal test parameter by the time of measurement.”	Changed to: “Summary statistics (no. of subjects, mean, standard deviation, median, minimum, and maximum) will be provided for each hormonal test parameter value and the change from baseline by the time of measurement.”	Add for evaluating the safety in more detail.
	Section 10.6.2 2)	Added: QTcF will be calculated using the following compensation formula. QTcF (ms) = QT interval / (RR interval) 1/3 .	Add the formula.
	Section 10.6.3 2) For 12-lead ECG parameters (observed values of RR interval,	Added: For 12-lead ECG parameters (observed values of RR interval,	Add for clarification.

	QT interval, Fridericia's corrected QT interval [QTcF], QRS width, and PR interval, and their changes [ $\Delta$ QTcF, $\Delta$ QRS, and $\Delta$ PR]), observed value (HR) and change ( $\Delta$ HR) of heart rate, summary statistics and frequency distribution for each category will be summarized at each time point.	QT interval, Fridericia's corrected QT interval [QTcF], QRS width, and PR interval, and their changes from baseline [ $\Delta$ QTcF, $\Delta$ QRS, and $\Delta$ PR]), observed value (HR) and change from baseline ( $\Delta$ HR) of heart rate, summary statistics and frequency distribution for each category will be summarized at each time point.	
Section 10.6.3 “P-R (ms) (observed value)”	Changed to: “PR (ms) (observed value)”	Typo	
Section 10.6.3 “ $\Delta$ QTcF (ms) (change)”	Added: “ $\Delta$ QTcF (ms) (change from baseline)”	Add for clarification.	
Section 11.2 2) (1) [1]	Added: Subjects with at least one baseline neutralizing positive sample for anti-ONO-4538 antibodies including baseline positive ones.	Clarify the definition.	
Section 11.2 2) (2) [2] Persistent positive: Subjects with two or more samples collected at consecutive time points after the first dose of the investigational product and testing positive for anti-ONO-4538 antibodies with a minimum interval of 16 weeks between the first and last positive samples.	Change to: Persistent positive: Subjects with two or more samples collected at consecutive time points after the first dose of the investigational product and testing positive for anti-ONO-4538 antibodies with a minimum interval of 16 weeks (there is a time window for one week) between the first and last positive samples.	Add for evaluating the anti-drug antibody properly.	
Section 11.3	Added: “and totality”	Add for clarification.	
Section 12.3 Background factors and efficacy endpoint	Added: Percent change in tumor diameter of target lesion (%)	Add for clarification.	
Section 12.3 Vital signs	Deleted: Respiratory rate(beats/min)	Typo	
Section 12.3 12-lead ECG QRS complex (ms)	Change to: QRS width (ms)	Typo	
